[Part 2 of 2 of the document. The other parts are not shown.]

Revised Protocol Section Number, Heading and Page Number	Original Wording from Clinical Protocol Version 3 Date 25 Aug 2015 (Deleted wording is struck through and in bold)	Revised Wording from Clinical Protocol Amendment 3 (Clinical Protocol V4 05Dec16) (Revised wording is underscored and in bold)	Rationale for the amendment
Section 1 Protocol Synopsis p. 12 (Summary of Patient Eligibility Criteria)	
 • Patient has significantly impaired hepatic function at the screening visit (Visit 1) or the randomization visit (Visit 3), defined as any of the following: • Serum alanine aminotransferase (ALT) or aspartate aminotransferase (AST) > 5 × upper limit of normal (ULN). • Serum ALT or AST ≥ 3 × ULN or TBL* [serum total bilirubin] ≥ 2 × ULN or international normalized ratio [INR] > 1.5 (*TBL ≥ 2 × ULN exclusion will not apply for patients diagnosed with Gilbert's disease). • Serum ALT or AST ≥ 3 × ULN with the presence of fatigue, nausea, vomiting, right upper quadrant pain or tenderness, fever, rash, and/or eosinophilia (> 5%). 	
 • Patient has significantly impaired hepatic function at the screening visit (Visit 1) or the randomization visit (Visit 3), defined as any of the following: • Serum alanine aminotransferase (ALT) or aspartate aminotransferase (AST) > 5 × upper limit of normal (ULN). • TBL* [serum total bilirubin] ≥ 2 × ULN or international normalized ratio [INR] > 1.5 (*TBL ≥ 2 × ULN exclusion will not apply for patients diagnosed with Gilbert's disease). • Serum ALT or AST ≥ 3 × ULN with the presence of fatigue, nausea, vomiting, right upper quadrant pain or tenderness, fever, rash, and/or eosinophilia (> 5%). This criterion can only be confirmed once 	
Previous wording was contradictory.

Revised Protocol Section Number, Heading and Page Number	Original Wording from Clinical Protocol Version 3 Date 25 Aug 2015 (Deleted wording is struck through and in bold)	Revised Wording from Clinical Protocol Amendment 3 (Clinical Protocol V4 05Dec16) (Revised wording is underscored and in bold)	Rationale for the amendment				
	This criterion can only be confirmed once the laboratory results are available.	the laboratory results are available.					
Section 1 Protocol Synopsis p. 13 (Criteria for Withdrawal)	
 ALT or AST > 3 × ULN or (TBL* > 2 × ULN or INR > 1.5). (*TBL > 2 × ULN exclusion will not apply for patients diagnosed with Gilbert’s disease). 	
 ALT or AST > 3 × ULN and (TBL* > 2 × ULN or INR > 1.5). (*TBL > 2 × ULN exclusion will not apply for patients diagnosed with Gilbert’s disease). 	Wording amended to reflect the FDA DILI guidelines accurately				
Definition of Terms p. 37	
 
 Baseline	The 28-day (±3 days) period from screening to randomization	
 
	Baseline	The 28-day (±3 days) period from screening to randomization	
 
 Baseline	The 28-day (±3 days) period from screening to randomization	
 
	Baseline	The 28-day (± 3 days) period from screening to randomization	Error, there is no -3 day window for this visit
Baseline	The 28-day (±3 days) period from screening to randomization						
Baseline	The 28-day (± 3 days) period from screening to randomization						
Section 3.4 Clinical Hypothesis p. 45-46	
The primary clinical hypothesis is that there will be a difference between 50 mg/kg/day GWP42003-P and placebo in their effect on mean focal seizure frequency as measured by analysis of covariance (ANCOVA). The mean treatment difference would need to be at least 35% in order to achieve a clinically relevant decrease in focal seizure
	
The primary clinical hypothesis is that there will be a difference between the GWP42003-P dose groups and placebo in their effect on focal seizure frequency.
	More concise				

Revised Protocol Section Number, Heading and Page Number	Original Wording from Clinical Protocol Version 3 Date 25 Aug 2015 (Deleted wording is struck through and in bold)	Revised Wording from Clinical Protocol Amendment 3 (Clinical Protocol V4 05Dec16) (Revised wording is underscored and in bold)	Rationale for the amendment
	frequency ⁵⁰ :		
Section 5.3.1 Packaging and Labeling p. 55		The IMP labels for the blinded phase and the open-label phase of the trial will have different colors, so these can be easily distinguished by the patients.	Additional text added for clarity
Section 6.2 Exclusion Criteria p. 59	
 • Patient has significantly impaired hepatic function at the screening visit (Visit 1) or the randomization visit (Visit 3), defined as any of the following: 
 • Serum alanine aminotransferase (ALT) or aspartate aminotransferase (AST) > 5 × upper limit of normal (ULN). • Serum ALT or AST ≥ 3 × ULN or TBL* [serum total bilirubin] ≥ 2 × ULN or international normalized ratio [INR] > 1.5 (*TBL ≥ 2 × ULN exclusion will not apply 	
 • Patient has significantly impaired hepatic function at the screening visit (Visit 1) or the randomization visit (Visit 3), defined as any of the following: 
 • Serum alanine aminotransferase (ALT) or aspartate aminotransferase (AST) > 5 × upper limit of normal (ULN). • TBL* [serum total bilirubin] ≥ 2 × ULN or international normalized ratio [INR] > 1.5 (*TBL ≥ 2 × ULN exclusion will not apply for patients diagnosed with Gilbert's 	Previous wording was contradictory.

Revised Protocol Section Number, Heading and Page Number	Original Wording from Clinical Protocol Version 3 Date 25 Aug 2015 (Deleted wording is struck through and in bold)	Revised Wording from Clinical Protocol Amendment 3 (Clinical Protocol V4 05Dec16) (Revised wording is underscored and in bold)	Rationale for the amendment
	
for patients diagnosed with Gilbert’s disease).
 
 • Serum ALT or AST $\geq 3 \times$ ULN with the presence of fatigue, nausea, vomiting, right upper quadrant pain or tenderness, fever, rash, and/or eosinophilia (> 5%). 
This criterion can only be confirmed once the laboratory results are available.
	
disease).
 
 • Serum ALT or AST $\geq 3 \times$ ULN with the presence of fatigue, nausea, vomiting, right upper quadrant pain or tenderness, fever, rash, and/or eosinophilia (> 5%). 
This criterion can only be confirmed once the laboratory results are available.
	

Section 8.1.2 Dose Escalation and Dose Adjustments p. 64-66
		
Table 8.1.2-2 is an example of the OLE transition (Visit B1 to Visit B2) for patients transitioning from each group of the randomized phase.
 
Table 8.1.2-2 (see amended figures and tables, page 26)
 
Following completion of the blinded transition patients may complete a three-week titration up to a
	
Additional text added to clarify how the transition between the double-blind phase and the Open-label phase works

Revised Protocol Section Number, Heading and Page Number	Original Wording from Clinical Protocol Version 3 Date 25 Aug 2015 (Deleted wording is struck through and in bold)	Revised Wording from Clinical Protocol Amendment 3 (Clinical Protocol V4 05Dec16) (Revised wording is underscored and in bold)	Rationale for the amendment
		
target dose of 50 mg/kg/day. Beginning at 25 mg/kg/day the dose will increase in increments of 2.5 mg/kg/day every two days (Table 8.1.2-3).
 
Table 8.1.2-3
 
(see amended figures and tables, page 26)
	

Section 9.1.2.7 Visit B6 (Day 183) p. 80
	
The following observations will be made at Visit B6: concomitant medications, (including AEDs), physical examination (including height and body weight), Tanner Staging (for patient aged 10-17 years [inclusive], or earlier if clinically indicated by onset of menarche or other signs of precocious puberty, details of menstruation (for females), ECG, vital signs, epilepsy-related hospitalizations and AEs.
	
The following observations will be made at Visit B6: concomitant medications, (including AEDs), physical examination (including height and body weight), details of menstruation (for females), ECG, vital signs, epilepsy-related hospitalizations and AEs.
	
Error, this assessment is not done at Visit B6

Revised Protocol Section Number, Heading and Page Number	Original Wording from Clinical Protocol Version 3 Date 25 Aug 2015 (Deleted wording is struck through and in bold)	Revised Wording from Clinical Protocol Amendment 3 (Clinical Protocol V4 05Dec16) (Revised wording is underscored and in bold)	Rationale for the amendment
Section 9.2.9 Clinical Laboratory Sampling Table 9.2.9-1 Biochemistry, Hematology, Urinalysis and THC Screen p. 88		Creatine Kinase (CK)	CK has been added to the battery of serum biochemistry tests
Section 10 Withdrawal p. 102	
 ALT or AST > 3 × ULN or (TBL* > 2 × ULN or INR > 1.5) (*TBL > 2 × ULN exclusions will not apply for patients diagnosed with Gilbert's disease) 	
 ALT or AST > 3 × ULN and (TBL* > 2 × ULN or INR > 1.5) (*TBL > 2 × ULN) 	Wording amended to reflect the FDA DILI guidelines accurately
Section 12.8 Potential Cases of Drug-induced Liver Injury p. 110	
 ALT or AST > 3 × ULN or (TBL* > 2 × ULN or INR > 1.5) (*TBL > 2 × ULN exclusions will not apply for patients diagnosed with Gilbert's disease) 	
 ALT or AST > 3 × ULN and (TBL* > 2 × ULN or INR > 1.5) (*TBL > 2 × ULN) 	Wording amended to reflect the FDA DILI guidelines accurately

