2.9 Changes requested by the Medicines and Healthcare Products Regulatory Agency

In response to a number comments from the Medicines and Healthcare Products Regulatory Agency, the following changes have been included within this amendment:

- Amend the wording included in the exclusion and withdrawal criteria involving liver enzyme monitoring to stipulate that patients with “Serum ALT or AST $\geq 3 \times$ ULN **or** (TBL [serum total bilirubin] $\geq 2 \times$ ULN or international normalized ratio [INR] > 1.5)” should be excluded from the trial and that patients with “ALT or AST $> 3 \times$ ULN **or** (TBL* $> 2 \times$ ULN or INR > 1.5)” should be withdrawn from the trial.
- For patients with Gilbert’s disease, a raised TBL would be considered normal and not a cause of exclusion or withdrawal unless ALT or AST were also elevated.
- In the UK, in order to demonstrate safety before exposing the younger patients to treatment, enrolment of patients between the ages of 12 and 23 months will only commence once 15 patients over the age of 23 months have been dosed for a minimum of 4 weeks and no new safety issues have been observed.
- Monthly pregnancy tests will be included.

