Section 12.8 Potential Cases of Drug-Induced Liver Injury p. 109	
(...)
 
 ALT or AST > 3 × ULN and (TBL > 2 × ULN or INR > 1.5). 
(...)
 
The Investigator will arrange for the patient to return to the investigational center as soon as possible (within 24 hours of notice of abnormal results) for repeat assessment of ALT, AST, TBL and alkaline phosphatase levels, detailed history and physical examination. Patients should be followed up in this way until all abnormalities have normalized (in the Investigator’s opinion) or returned to the baseline state.
	
(...)
 
ALT or AST > 3 × ULN or (TBL* > 2 × ULN or INR > 1.5). (*TBL > 2 × ULN exclusion will not apply for patients diagnosed with Gilbert’s disease).
 
(...)
 
The Investigator will arrange for the patient to return to the investigational site as soon as possible (within 24-48 hours of notice of abnormal results) for repeat assessment of ALT, AST, TBL, alkaline phosphatase and gamma-glutamyl transferase, detailed history and physical examination. Patients should be followed up in this way until all abnormalities have normalized (in the Investigator’s opinion) or returned to the baseline state; however, if the above transaminase elevation criteria are confirmed by the first set of follow-up laboratory tests, the patient must be withdrawn from the trial.
	
See Section 2.9
 
See Section 2.5
 
See Section 2.5

Revised Protocol Section Number, Heading and Page Number	Original Wording from Clinical Protocol Version 2 Date 21 OCT 2015 (Deleted wording is struck through and in bold)	Revised Wording from Clinical Protocol Amendment 2 (Clinical Protocol V3 25Aug16) (Revised wording is underscored and in bold)	Rationale for the amendment

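### Amendment 3 (V4) prints the mandatory liver withdrawal criterion with a Gilbert's disease exemption in the synopsis and without one in Sections 10 and 12.8

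*Protocol*

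**What the plan says.** The Amendment 3 table of amended text gives the V4 wording of the same withdrawal criterion in three rows.

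- **Section 1, Synopsis, Criteria for Withdrawal.** The rule is "ALT or AST > 3 × ULN and (TBL* > 2 × ULN or INR > 1.5", and the asterisk leads to the note "TBL > 2 × ULN exclusion will not apply for patients diagnosed with Gilbert’s disease".
- **Section 10, Withdrawal, and Section 12.8, Potential Cases of Drug-induced Liver Injury.** The rule is the same, but rule and note together read "TBL* > 2 × ULN or INR > 1.5) (*TBL > 2 × ULN", after which the bracket closes. Gilbert's disease is not mentioned. The V3 wording printed beside it did carry the exemption.

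All three rows give the same reason for the change, namely alignment with the FDA guidance on drug-induced liver injury. None of them comments on Gilbert's disease.

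The only statement of what the exemption is for is in Amendment 2, Section 2.9. In Gilbert's disease, it says, "a raised TBL would be considered normal and not a cause of exclusion or withdrawal unless ALT or AST were also elevated".

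Amendment 2, Section 12.8, lets the site repeat the tests, and then: "if the above transaminase elevation criteria are confirmed by the first set of follow-up laboratory tests, the patient must be withdrawn from the trial".

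**The concern.** A mandatory stopping criterion should give one answer for one set of laboratory results. As printed, a site working from the synopsis and a site working from Section 10 or 12.8 can reach opposite conclusions about the same Gilbert's patient.

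The change of conjunction makes this more than a missing phrase. Under the V4 rule, raised transaminases are a precondition for withdrawal. An exemption attached to the bilirubin limb can then matter only in a patient whose transaminases are already above 3 × ULN. That is the patient for whom Section 2.9 of Amendment 2 withholds the exemption. At stake is consistent handling of a possible liver injury signal in a small group of patients.

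**Working it through.** No sample size, power or alpha figure is involved, and the plan gives no number to reproduce. The check is a truth table.

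**Inputs.** A: ALT or AST > 3 × ULN. T: TBL > 2 × ULN. I: INR > 1.5. G: Gilbert's disease. The thresholds come from the Amendment 3 wording.

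**Rules.**
- Synopsis, V4: A and [(T and not G) or I].
- Sections 10 and 12.8, V4: A and (T or I).
- V3, with exemption: A or (T and not G) or I.
- V3, had there been no exemption: A or T or I.

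**All eight states for a Gilbert's patient (G = yes); W = criterion met.**

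| A | T | I | Synopsis V4 | Sections 10/12.8 V4 | V3 with exemption | V3 without |
|---|---|---|---|---|---|---|
| yes | yes | yes | W | W | W | W |
| yes | yes | no | – | W | W | W |
| yes | no | yes | W | W | W | W |
| yes | no | no | – | – | W | W |
| no | yes | yes | – | – | W | W |
| no | yes | no | – | – | – | W |
| no | no | yes | – | – | W | W |
| no | no | no | – | – | – | – |
| **Total W** | | | **2** | **3** | **6** | **7** |

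**Results.**

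1. The two V4 wordings differ in 3 − 2 = 1 of 8 states: A yes, T yes, I no. For patients without Gilbert's disease the two rules are identical, with 3 of 8 states each.
2. Under V3 the exemption also changed one state (7 − 6 = 1), but the opposite one: T yes with A no. There ALT/AST was not above 3 × ULN. Under V4 it changes only the state with A yes.
3. In the V4 state, ALT/AST exceeds 3 × ULN. It therefore counts as elevated whether Section 2.9 means above ULN or above 3 × ULN, and on that text the exemption would not hold.
4. The repeat test does not settle the matter. It asks whether the criteria listed above it are confirmed, and which criteria those are is the open question.

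**After alignment.** If the synopsis exemption is deleted, all three places give 3 of 8 states and agree with Section 2.9. If the exemption is restored in Sections 10 and 12.8, all three give 2 of 8 and agree with one another, but not with Section 2.9.

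**The case against.** The strongest case against runs as follows. All the evidence is an amendment table, and the consolidated protocol text is not in the part available. The table is not fully verbatim. It dates V3 to August 2015 where Amendment 2 says August 2016, and its V3 cell for Section 10 has > where Amendment 2 printed ≥. A note that consists only of its own label looks like a sentence that lost its ending, in which case the exemption may have been meant to be uniform. Section 2.9 is rationale for V3's *or* rule, which Amendment 3 replaced. Finally, the withdrawal list is shown only in excerpt. If it also contains limbs for ALT/AST above 5 × ULN and for symptoms, as the entry criterion does, the discordant zone splits into 2 × 2 = 4 cells. Three of these would be withdrawn under either wording, leaving only the asymptomatic patient between 3 and 5 × ULN.

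Much of this stands as limitation. It does not remove the discrepancy. The comparison is between revised wordings within one amendment, not between a log and later text. The cut-off note appears identically in two separate rows. Whether it is a deliberate deletion or a slip, the printed rules disagree.

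A reader might infer that the synopsis is proven to be the wrong version. The documents do not go that far. Section 2.9 supports that direction, but it is not V4 rule text, and Amendment 3 gives no reason that mentions Gilbert's disease.

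A reader might also infer that the entry criterion needs correcting, because it grants a Gilbert's exemption without the Section 2.9 condition. That is not supported either. The synopsis eligibility summary and Section 6.2 agree with each other in V4, and narrowing that exemption would be a design choice.

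**Conclusion.** The inconsistency holds for this one criterion: the V4 wording in the synopsis and that in Sections 10 and 12.8 give opposite answers for a Gilbert's patient with ALT/AST > 3 × ULN, TBL > 2 × ULN and INR ≤ 1.5. The move from *or* to *and* also confines the exemption to the situation in which the only stated intent says it should lapse.

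Severity is minor. The conclusion rests on the Amendment 3 table reflecting the operative text, which has to be confirmed. It concerns this criterion and not a patient's overall disposition, since other withdrawal criteria or an investigator's decision may still remove the patient. It would therefore be too strong to say that such patients will stay on drug. The documents give neither the prevalence of Gilbert's disease nor the rate of such laboratory results, so no patient count is offered. No effect on the primary analysis is claimed.

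**What to change.** Check the consolidated synopsis, Section 10 and Section 12.8 first. If the mismatch is there, print one identical rule in all three places.

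- **Default, in line with Amendment 2, Section 2.9:** delete the Gilbert's note and its asterisk from the synopsis withdrawal criterion, and remove the asterisk and the leftover fragment in Sections 10 and 12.8.
- **Alternative:** if the sponsor documents that the exemption is meant to hold despite raised ALT/AST, restore the full sentence in Sections 10 and 12.8 and state the reason.

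The entry criterion stays as it is. The cost is one sentence in the synopsis and one fragment in each of two sections, made at the next amendment or administrative correction, with no added procedures.

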APPENDIX 1 AMENDED FIGURES AND TABLES

Amended Figure from Clinical Protocol V4 05Dec16

(Deleted wording is struck through and in bold; amended wording is underlined and in bold)

Table 8.1.2-2

Table 8.1.2-2 Blinded Transition						
	Patients randomised to 25 mg/kg/day group		Patients randomised to 50 mg/kg/day group		Patients randomised to placebo group	
Day Blinded Transition/OLE	Blinded	Open label	Blinded	Open label	Placebo	Open label
1	25	0	50	0	0	0
2	22.5	0	45	0	0	0
3	20	5	40	5	0	5
4	17.5	5	35	5	0	5
5	15	10	30	10	0	10
6	12.5	10	25	10	0	10
7	10	15	20	15	0	15
8	7.5	15	15	15	0	15
9	5	20	10	20	0	20
10	2.5	20	5	20	0	20
11	0	25	0	25	0	25
12	0	25	0	25	0	25
13	0	25	0	25	0	25
14	0	25	0	25	0	25

Table 8.1.2 – 3 OLE Titration Schedule

OLE Day	Blinded Dose (mg/kg/day)
15 (Visit B2)	26.25
16	27.5
17	30
18	30
19	32.5
20	32.5
21	35
22	35
23	37.5
24	37.5
25	40
26	40
27	42.5
28	42.5
29	45
30	45
31	47.5
32	47.5
33	50
34	50
35	50
36 (Visit B3)	50

Study Title: A double-blind, randomized, placebo-controlled study to investigate the efficacy and safety of cannabidiol (GWP42003-P, CBD) as add-on therapy in patients with tuberous sclerosis complex who experience inadequately-controlled seizures

Study Code: GWEP1521

EudraCT Number: 2015-002154-12

CLINICAL PROTOCOL AMENDMENT NUMBER: 2

**to be incorporated into the Protocol, creating
CLINICAL PROTOCOL V3 25Aug16**

**GW Research Ltd
[name]
United Kingdom**

Tel: PPD
Fax: PPD

Confidentiality Statement

This document contains confidential information of GW Research Ltd (GW) that must not be disclosed to anyone other than the recipient study staff and members of the institutional review board or independent ethics committee. This information cannot be used for any purpose other than the evaluation or conduct of the clinical investigation without the prior written consent of GW.

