	
Following completion of the blinded phase patients will be invited to continue to receive GWP42003-P in an OLE.
 
Those patients opting not to enter the OLE will complete a 10-day taper period (down-titrating 10% per day for 10 days).
 
Open-label Extension Transition:
 
In order to maintain consistent exposure to IMP and maintain the integrity of the blind, patients will enter a 2-week blinded transition to the OLE. OLE IMP will be titrated up to 25 mg/kg/day whilst blinded IMP is simultaneously tapered down to zero. All patients will complete the transition and enter the OLE taking 25 mg/kg/day GWP42003-P:
 
• Patients from the placebo group will titrate up to 25 mg/kg/day GWP42003-P.• Patients from the 25 mg/kg/day GWP42003-P group will continue to take 25 mg/kg/day GWP42003-P.• Patients from the 50 mg/kg/day GWP42003-P group will taper down (10% per day) to 25 mg/kg/day GWP42003-P. 
Safety telephone calls will be completed every two days throughout the open label extension transition. If the call falls on a weekend, it is permitted to schedule the call for the Friday before or Monday after the weekend instead.
 
Open-label Extension:
 
The OLE consists of a 3-week titration period followed by a maintenance period and a 10-day taper period. The OLE treatment period will last for a maximum of 1 year.
 
Following titration according to the titration schedule, patients will continue with their optimal GWP42003-P dose. However, investigators may decrease the dose if a patient experiences intolerance, or increase the dose to a maximum of 50 mg/kg/day if required for better seizure control, until the optimal dose is found. Dose increases above 25 mg/kg/day are recommended to be done slowly, with maximum increments of 2.5 mg/kg/day every two days. Patients whose dose has been decreased can have their dose increased again provided there is adequate tolerance. Safety telephone calls will be completed every two days throughout the OLE titration and one week after the end of titration. If the call falls on a weekend, it is permitted to schedule the call for the Friday before or Monday after the weekend instead. If seizure freedom is achieved with use of GWP42003-P during the study, the investigator should consider reducing the dose of concomitant AEDs after six months of seizure freedom.

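### In the 25 mg/kg/day group, the blinded-transition table adds to 22.5 mg/kg/day on five days for which the text says the dose continues at 25

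*Protocol*

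**What the plan says.** The synopsis in Protocol Amendment 2 (version 3), under the open-label extension transition, gives the purpose: "In order to maintain consistent exposure to IMP and maintain the integrity of the blind, patients will enter a 2-week blinded transition to the OLE". It gives the mechanism: "OLE IMP will be titrated up to 25 mg/kg/day whilst blinded IMP is simultaneously tapered down to zero". It then takes each randomized group in turn. For the lower dose group it says: "Patients from the 25 mg/kg/day GWP42003-P group will continue to take 25 mg/kg/day GWP42003-P". For the higher dose group: "Patients from the 50 mg/kg/day GWP42003-P group will taper down (10% per day) to 25 mg/kg/day GWP42003-P". Placebo patients titrate up to 25 mg/kg/day. The synopsis in Amendment 1 carries the same three statements.

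Amendment 3 (version 4) added a schedule to Section 8.1.2, captioned "Table 8.1.2-2 Blinded Transition"; the figures are in its Appendix 1. The amended text says the table "is an example of the OLE transition (Visit B1 to Visit B2) for patients transitioning from each group of the randomized phase". The stated reason for adding it is to clarify how the move from the double-blind to the open-label phase works. The table has a blinded and an open-label column for each randomized group, with the first pair headed "Patients randomised to 25 mg/kg/day group".

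**The concern.** The table was added to illustrate the transition rule, and for one group it does not follow that rule. The text keeps the 25 mg/kg/day group at 25 while one product replaces the other. The table lowers the blinded product every day but raises the open-label product only every second day, so on alternate days the reduction has not yet been made up. The protocol then states two different daily doses for the same patients at the switch to open-label drug, while safety calls are being made every two days. Any dosing tool or exposure summary built from the protocol can agree with only one of them.

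**Working it through.** **Inputs.** Both columns come from Table 8.1.2-2 in Appendix 1 of Amendment 3, for the 25 mg/kg/day group. The stated dose of 25 mg/kg/day comes from the transition text in the Amendment 2 synopsis.

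**Formula.** Total dose on a day = blinded dose + open-label dose. Addition is the right operation because the text has one product going up while the other goes down. The other readings fail: the blinded column alone falls from 25 to 0, and the open-label column alone rises from 0 to 25. Neither is a continued 25.

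| Day | Blinded | Open label | Total | Text |
|---|---|---|---|---|
| 1 | 25 | 0 | 25 | 25 |
| 2 | 22.5 | 0 | 22.5 | 25 |
| 3 | 20 | 5 | 25 | 25 |
| 4 | 17.5 | 5 | 22.5 | 25 |
| 5 | 15 | 10 | 25 | 25 |
| 6 | 12.5 | 10 | 22.5 | 25 |
| 7 | 10 | 15 | 25 | 25 |
| 8 | 7.5 | 15 | 22.5 | 25 |
| 9 | 5 | 20 | 25 | 25 |
| 10 | 2.5 | 20 | 22.5 | 25 |
| 11 to 14 | 0 | 25 | 25 | 25 |

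The stated 25 mg/kg/day is reproduced on Days 1, 3, 5, 7, 9 and 11 to 14. It is not reproduced on Days 2, 4, 6, 8 and 10.

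**Size.**
- Gap on an affected day: 25 − 22.5 = 2.5 mg/kg/day, and 2.5 / 25 = 10%.
- Mean over Days 1 to 10: (5 × 25 + 5 × 22.5) / 10 = 237.5 / 10 = 23.75 mg/kg/day.
- Mean over Days 1 to 14: (237.5 + 4 × 25) / 14 = 337.5 / 14 = 24.1 mg/kg/day, which is 12.5 / 350 = 3.6% below a constant 25.

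**The 50 mg/kg/day group, for comparison.** The blinded column is 50, 45, 40, 35, 30, 25, 20, 15, 10, 5, 0. Each step is 5, and 5 / 50 = 10%. The blinded product therefore tapers by 10% of the starting dose per day down to zero, as the mechanism sentence describes. The totals on Days 1 to 11 are 50, 45, 45, 40, 40, 35, 35, 30, 30, 25, 25.

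**Versions.** The table is version 4 text and the sentence is version 3 text. Amendment 2 shows the lead-in to the group list, ending in a colon, at synopsis p. 15 and at Section 4.1, pp. 47–48. The rows of Amendment 3 that are shown go from synopsis p. 13 to the definitions on p. 37, and from Section 3.4 (pp. 45–46) to Section 5.3.1 (p. 55). They list no change at either place.

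**The case against.** **The two sources are different versions.** This is the best objection. The consolidated version 4 protocol is not shown, nor are any Amendment 3 rows before synopsis p. 12. It cannot be proved here that the sentence still stands beside the table. But no visible row changes the list in Section 4.1, and the table was added for clarity, not to change the rule. The caveat stands; it does not remove the point.

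**The table is only an example, and the list only summarizes how each group reaches 25.** All groups are indeed at 25 from Day 11. But the example is set out by randomized group, it is the only day-by-day transition schedule shown, and the sentence for this group says the patients continue on 25, not that they return to it.

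**Stronger readings that the documents do not support.**
- A reader might infer that the 50 mg/kg/day schedule is wrong too, because the total does not fall by 10% per day and reaches 25 on Day 10, not Day 6. No section gives Day 6. What is tapered, according to the mechanism sentence, is the blinded product, and that column does fall by 10% per day. A total of 25 on Day 6, when the blinded column alone is 25, would leave no open-label dose up to that day, contrary to the simultaneous titration.
- A reader might take the stated aim, "In order to maintain consistent exposure to IMP and maintain the integrity of the blind", as a promise of a constant daily dose. It covers all patients, including placebo patients going from 0 to 25 and the higher dose group coming down to 25, so it cannot mean that.
- A reader might conclude that sites dose from this table, or that dose by day will be misdescribed in the open-label data. Neither is stated. Amendment 2 has blinded-phase volumes calculated through the IVRS (Section 8.1.2) and recorded usage checked against the dose calculator and IVRS (Section 8.4). Patients record their study medication daily in a paper diary.

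**Conclusion.** For the 25 mg/kg/day group only, the table and the transition text state different daily doses: 22.5 against 25 mg/kg/day on Days 2, 4, 6, 8 and 10, a gap of 10% on those days and 3.6% over the two weeks. The row sums are exact and need no assumption beyond adding two products taken together. The conflict in the current protocol also assumes that the sentence survives into version 4, which the visible amendment rows indicate but do not prove.

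Severity is minor. The transition comes after the end of blinded treatment (Day 113), so the primary endpoint, the blinded comparison, the sample size and the type I error are not affected. The figures for the 50 mg/kg/day group are not part of the finding.

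**What to change.** Reconcile Table 8.1.2-2 with the transition text in the synopsis and in Section 4.1, so that both give the same daily dose for the 25 mg/kg/day group. Add a total-daily-dose column for each randomized group; that makes the sum visible and prevents the two from drifting apart again. Check that the dose calculator and IVRS produce the reconciled figures. Which figures apply is for the sponsor's clinical team to decide. The cost is an edit to one table or to the matching sentences, plus the check of the dosing tools. No analysis changes.
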